Upon signing the informed consent document, subjects will be randomized to either the immediate monitoring group or delayed monitoring group by random number generator. The random number generator uses Ruby's pseudo-random number generator functionality (PRNG) implemented as a modified Mersenne Twister with a period of 2**19937-1. The subject's group assignment will be sent to the STSI coordinating team. Continued eligibility of all randomized subjects for the study will be confirmed upon enrollment using Aetna databases for all inclusion and exclusion criteria.

For subjects randomized to the immediate monitoring group, the first Zio patch will be sent upon confirmation of continued eligibility. The first Zio patch will be worn by subjects in the immediate monitoring group during the first two weeks of the 4-month monitoring period. A second Zio patch will be sent to subjects in the immediate monitoring group for wear during the final two weeks of the 4-month monitoring period.

A subject will be considered withdrawn from the study if they inform the STSI study coordinating center that they wish to withdraw or if they have not initiated use of the first Zio patch after 3 notifications (e-mail/phone/e-mail) from the coordinating center.

Intention-to-treat analysis for the RCT will include all participants who are enrolled in the study according to their randomly assigned group (immediate monitoring or delayed monitoring) with the RCT follow-up time for subjects in the immediate monitoring group beginning at date of enrollment and ending at 4 months following date of enrollment or the time of completion of monitoring with their final patch, whichever is longest, and for subjects in the delayed monitoring group beginning at date of enrollment and ending at 4 months following the date of enrollment.

The per protocol analysis of the RCT will include immediate monitoring participants had analyzable data from the Zio patch for at least 30 continuous minutes any time during their assigned monitoring period and all participants in the delayed monitoring group who did not withdraw from the study prior to 4 months of follow-up.

Delayed Monitoring Group

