Subjects randomized to the delayed monitoring cohort for the RCT will be actively monitored following completion of the 4 month RCT follow-up period (for which they serve as unmonitored controls). Subjects in the delayed monitoring group will receive their first Zio patch 4 months following their date of enrollment. The first Zio patch will be worn during the first two weeks of the 4-month monitoring period. A second Zio patch will be sent to subjects in the delayed monitoring group for wear during the final two weeks of the 4-month monitoring period.

Matched Observational Cohort Study: Actively Monitored (Immediate and Delayed) vs. Matched Observational Controls

For the Matched Observational Cohort study, the actively monitored group will include all subjects in the RCT who were randomly assigned to either active monitoring period (immediate or delayed).

Two matched controls will be selected for each of the 2,100 actively monitored subjects in the RCT (1,050 immediate + 1,050 delayed) from 1) the pool of subjects from the original eligible cohort who continue to be eligible based on monthly database updates and did not receive an invitation to enroll. Matching will be performed using the following criteria:

- Sex (exact)
- Age (exact by year of birth)
- CHA₂DS₂ VASc score (exact score)

CHA₂DS₂ VASc scores are re-calculated for monitored subjects at time of enrollment (updating scores calculated for eligibility of original pool). CHA₂DS₂ VASc scores are re-calculated for the pools of potential matched controls following the monthly update of the Aetna claims database and immediately prior to application of the matching protocol. Actively monitored subjects and controls will be matched on these updated CHA₂DS₂ VASc scores. Exact matches are prioritized. Matching of CHA₂DS₂ VASc score \pm 1 will be the next option if 2 exact match controls are not found for a monitored subject.

Start date for determination of outcomes from Aetna databases for both monitored subjects and matched controls will be the date of enrollment of the monitored subject. End date for the analysis of prevalence of atrial fibrillation, initiation of anticoagulation and initiation of other AF-specific interventions will be 12 months from the actively monitored subject's date of enrollment (by exact month and day). End date for analysis of outcomes at 3 years will be 3 years from the actively monitored subject's date of enrollment (by exact month and day).

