For the Matched Observational Cohort Study, the ITT population will be all subjects enrolled in the RCT (actively monitored group=immediate monitoring + delayed monitoring) and their matched controls. The per protocol analysis will consist of 1) all subjects in the RCT had analyzable data from Zio patch monitoring of at least 30 continuous minutes during the RCT and who did not request removal from the observational follow-up at time of withdrawal and 2) their matched controls.

Matched Observational Cohort Study: Atrial Fibrillation Sub-population

The sub-population of subjects diagnosed with atrial fibrillation for the analyses of disease endpoints and hospitalization events will consist of subjects in the actively monitored group who received a new diagnosis of atrial fibrillation during active monitoring with the Zio patch or at any time during the 3 year follow-up by claims data and subjects in the matched observational control cohort who received a new diagnosis of atrial fibrillation based on claims data during the 3 year follow-up.

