We will use the same time to event analyses with 3 year follow-up to evaluate the same disease and hospitalization endpoints among the subset of subjects included in the matched observational cohort study who receive a diagnosis of atrial fibrillation during the study. All analyses will be performed as intention-to-treat with parallel exploratory analyses performed on per-protocol basis restricted to subjects enrolled in the monitoring group who underwent Zio patch monitoring.

Analysis of Safety Endpoints

For analysis of safety endpoints at 3 year follow-up, we will compare incidence of hospitalization for bleeding per person-years of follow-up between the actively monitored group and the matched observational control group. Hospitalizations for bleeding will also be characterized by length of stay. Other safety outcomes will be characterized for the period of active monitoring in the active monitoring group only. These include Incidence of non-AF, but other actionable heart rhythms captured by the Zio patch device, specifically: 1) Atrial Tachycardia with variable block of > 30 seconds; 2) Ventricular Tachycardia >5 beats; 3) Pauses \geq 5 seconds; and 4) AV block. We will also characterize early discontinuation of active monitoring in monitored cohort by cause and time to event.

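### Read literally, the observational per-protocol rule (patch data during the RCT) shuts out the whole delayed arm; probably a drafting error, affecting supplementary analyses only

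*SAP*

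**What the plan says.** All of the following is in the SAP.

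- **Who is monitored (section 4, Matched Observational Cohort Study).** The actively monitored group is everyone randomized to either monitoring period. "Two matched controls will be selected for each" of the "2,100 actively monitored subjects in the RCT (1,050 immediate + 1,050 delayed"). The intention-to-treat definition again names both arms.
- **Per-protocol rule (section 4, same part).** RCT subjects need "analyzable data from Zio patch monitoring of at least 30 continuous minutes during the RCT" and must not have asked to be removed from observational follow-up. Their matched controls come with them.
- **RCT window (section 4, Randomized Controlled Trial Population).** RCT follow-up is set by arm. The immediate arm's window extends to its final patch if that is later than 4 months. The delayed arm's window is stated as: "for subjects in the delayed monitoring group beginning at date of enrollment and ending at 4 months following the date of enrollment". It has no extension.
- **When the delayed arm is monitored (section 4, Delayed Monitoring Group).** These subjects "will be actively monitored following completion of the 4 month RCT follow-up period". The timing is explicit: "Subjects in the delayed monitoring group will receive their first Zio patch 4 months following their date of enrollment". Protocol section 4, Study Flow, gives the same timing.
- **Use of the set (section 7).** Every 12-month analysis is run first by intention-to-treat and second per protocol. The 3-year per-protocol analyses are parallel and exploratory, and are described as "restricted to subjects enrolled in the monitoring group who underwent Zio patch monitoring", with no RCT window.

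**The concern.** The three section 4 statements do not fit together. Patch data must fall during the RCT, the delayed arm's RCT period ends at 4 months, and its patches start after that. A programmer who filters recording dates on the stated window would find no qualifying delayed-arm subject, however long the patches were worn. A colleague who takes RCT to mean the whole study would keep that arm. The two sets would differ by half the cohort.

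The loss is more than one of size. Outcomes for all monitored subjects are counted from enrollment, so the delayed arm carries about 4 unscreened months that the immediate arm does not. If the per-protocol set holds only the immediate arm while the intention-to-treat set pools both, a difference between the two results mixes patch adherence with the timing of screening.

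This is separate from the disagreement between SAP sections 4 and 7 over whether the RCT's own per-protocol set needs 30 continuous or 30 total minutes. Settling that would leave this problem in place.

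**Working it through.** **1. Who can qualify under the literal window**

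| | Immediate arm | Delayed arm |
|---|---|---|
| RCT follow-up ends (SAP 4) | 4 months or final patch, whichever is later | 4 months after enrollment |
| First patch (SAP 4) | once eligibility is reconfirmed | 4 months after enrollment, once RCT follow-up is complete |
| Patch time inside the window | all of it | none |

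- Monitored subjects: 1,050 + 1,050 = 2,100, as the SAP states. Delayed-arm subjects able to qualify: 0 of 1,050. Share lost: 1,050 / 2,100 = 50%.
- Controls at two per subject: 2 × 2,100 = 4,200 in all. Those lost with the delayed arm: 2 × 1,050 = 2,100.

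**2. The plan's 12-month power, reproduced**

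Inputs from SAP section 7: 7% versus 2%, 2,000 versus 4,000, two-sided alpha 0.05. For two proportions, power = Φ[(|p1 − p2| − 1.96·SE0) / SE1], with SE0 from the pooled rate and SE1 from the separate rates.

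- Pooled rate = (0.07 + 2 × 0.02) / 3 = 0.0367
- SE0 = sqrt(0.0367 × 0.9633 × (1/2,000 + 1/4,000)) = 0.00515
- SE1 = sqrt(0.07 × 0.93/2,000 + 0.02 × 0.98/4,000) = 0.00612
- (0.05 − 1.96 × 0.00515) / 0.00612 ≈ 6.5, so power exceeds 0.999. The SAP says above 99%, so it agrees.

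**3. Effect on 12-month precision**

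SE = sqrt(0.07 × 0.93/n1 + 0.02 × 0.98/n2); half-width = 1.96 × SE.

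| Set | n1 / n2 | SE (points) | 95% half-width (points) | Power |
|---|---|---|---|---|
| Both arms | 2,100 / 4,200 | 0.597 | 1.17 | >0.999 |
| Immediate arm only | 1,050 / 2,100 | 0.845 | 1.66 | >0.999 |

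The SE ratio is 0.845 / 0.597 = 1.41 (√2), an increase of 41%. The sizes are upper bounds, because subjects without 30 continuous minutes leave either set. If they leave at the same rate in both arms, the ratio is unchanged.

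**4. Three years, only if the section 4 rule governed**

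The SAP plans the AF sub-population at 200 versus 400, with event rates of 5% versus 12% and 81% power. The two-proportion formula gives 0.812, and a log-rank simulation with the protocol's cumulative rates at 6, 15 and 36 months gives 0.826. Both are close to the stated figure. Halving to 100 versus 200 cuts expected events from 200 × 0.05 + 400 × 0.12 = 58 to 29, and power to about 0.49 by either method. This assumes the planning rates hold in the per-protocol set and the sub-population halves in proportion.

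**The case against.** The strongest reply is that RCT here names the whole randomized study. When the SAP means the 4-month window it usually says RCT follow-up time or period. Section 4 counts the delayed arm among the actively monitored subjects in the RCT, and section 7 describes the monitored group as coming from the randomized trial. The per-protocol rule itself starts from all RCT subjects, directly after naming both arms. Section 7 also gives an intention-to-treat follow-up that runs to the final patch without separating the arms, which taken literally would cover the delayed arm's patches.

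Most of this stands as evidence of intent: the exclusion was very probably not meant. It does not make the text safe. Section 7 also speaks of a 4-month RCT, and section 4 defines the delayed arm's window and places its monitoring after it. The unsplit follow-up sentence conflicts with section 4 and with section 7's own restriction of the primary analysis to the first 4 months. Relying on it would count patch-detected AF in the unmonitored control arm.

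Two stronger inferences are tempting:

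- *That both the 12-month and 3-year per-protocol analyses, as written, cover only the immediate arm.* At 3 years section 7 describes the set as those who underwent patch monitoring, with no window. That is a conflict between two sections, not an established exclusion, so the fall in power to 0.49 is conditional.
- *That the 12-month conclusion is in jeopardy.* A half-width of 1.66 points around an expected 5-point difference does not threaten it.

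**Conclusion.** The concern holds in limited form. On the SAP's own window for the delayed arm, the literal rule removes up to 1,050 of 2,100 monitored subjects and 2,100 of 4,200 controls from the observational per-protocol set, against the two-arm definition of the monitored group. The SAP's usage of RCT is not uniform, so this is best treated as a probable drafting error.

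At 12 months the cost is precision (half-width about 1.17 to 1.66 points under the planning rates) and, more importantly, a per-protocol result that cannot be set cleanly beside the pooled intention-to-treat result. At 3 years the finding is that sections 4 and 7 disagree. Only supplementary analyses are touched; the primary RCT comparison and every intention-to-treat analysis are unaffected.

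The sizes assume the planned 1:1 split, full 2:1 matching and, for precision, that the planning rates apply in the per-protocol set.

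**What to change.** In the observational per-protocol definition in SAP section 4, replace *during the RCT* with *any time during their assigned monitoring period (immediate or delayed)*. The first part is the phrase section 4 already uses for the immediate arm in the RCT per-protocol set. Do not add a 4-month cap: section 4 expects some final patches to finish later than 4 months after enrollment, and a cap could drop valid recordings.

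Then have the 12-month and 3-year observational per-protocol analyses in section 7 refer to that definition, so that one set is used throughout.

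The cost is one phrase and two cross-references. No new data are needed to apply the window, because patch recording start dates and analyzable time are already listed in SAP section 2.

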5. ENDPOINTS AND COVARIATES

[Data source in brackets]

Primary Endpoint

1. Atrial Fibrillation/Flutter: new diagnosis of atrial fibrillation or atrial flutter defined as:
 - a. ≥ 30 seconds of atrial fibrillation or flutter diagnosed and adjudicated on the iRhythm output (monitored cohort) [PI Diagnosis Database]
 - i. Date
 - ii. Duration
 - b. Claim for atrial fibrillation/atrial flutter with ICD-9 code 427.1 or 427.2 or ICD-10 code I48.91 or I48.9 [Aetna Claims Data; Aetna Medical Case]
 - i. Date

Secondary Endpoints

1. Atrial Fibrillation/Flutter: HPD algorithm [Aetna HPD Database]
2. Anticoagulation: Drug NDC codes for new refill for any:
 - a. Anticoagulant (dabigatran, rivaroxaban, apixaban) or
 - i. Date
 - b. P2Y12 Antagonists (clopidogrel, prasugrel or ticagrelor) without a new diagnosis of acute coronary syndrome
 - i. Date
4. Other AF-related therapies (i.e. antiarrhythmic agents excluding beta-blockers and calcium channel blockers, cardioversions, ablation procedures or hospitalizations with a primary diagnosis of AF)
5. UtilizationCommented [[name]]: Need to further define
3. Stroke-related visits during follow-up [Aetna Medical Case]
 - a. Inpatient
 - b. ER
 - c. Time to first stroke-related event (Inpatient or ER)
4. Myocardial infarction-related visits during follow-up [Aetna Medical Case]
 - a. Inpatient
 - b. ER
 - c. Time to first myocardial infarction-related event (Inpatient or ER)
5. Systemic thromboembolism-related visits during follow-up [Aetna Medical Case]
 - a. Inpatient
 - b. ER
 - c. Time to first systemic thromboembolism-related event (Inpatient or ER)
6. Death (Medicare population): [Aetna ATV; Aetna Membership Table]
 - a. Time to death (within 1 month of date)

- b. Cause of death
- 7. All-Cause Hospital Admissions [Aetna Medical Case]
 - a. Total number
 - b. Total length of stay
 - c. Individual admissions
 - i. Primary diagnosis
 - ii. Date
 - iii. Length of stay

Safety Endpoints

- 1. Hospital admission for primary bleeding diagnosis: [Aetna]
- 2. Incidence of non-AF, but other actionable heart rhythms captured by device (and confirmed by PI) [PI Diagnostic Database]
 - a. Atrial Tachycardia with variable block of > 30 seconds
 - b. Ventricular Tachycardia >5 beats
 - c. Pauses \geq 5 seconds
 - d. AV block
- 3. Early discontinuation of active monitoring in monitored cohort [Scripps Study Database]
 - a. Date of discontinuation
 - b. Cause of discontinuation

Exploratory Endpoint (Amiigo)

- 1. Correlation between Amiigo-detected AF and Zio patch detected AF with rate of true and false positives during overlapping monitoring.

Other Endpoints

- 1. Followup Count of All-Cause ER Visits [Aetna Medical Case]
- 2. Followup Count of All-Cause IP Visits [Aetna Medical Case]
- 3. Followup Total Length of Stay for All-Cause IP Visits [Aetna Medical Case]
- 4. Followup Count of All All-Cause Visits (IP and ER) [Aetna Medical Case]
- 5. Followup Time to First All-Cause Event (IP or ER) [Aetna Medical Case]
- 6. Followup Count of Stroke-Related ER Visits [Aetna Medical Case]
- 7. Followup Count of Stroke-Related IP Visits [Aetna Medical Case]
- 8. Followup Total Length of Stay for Stroke-Related IP Visits [Aetna Medical Case]
- 9. Followup Count of All Stroke-Related Visits (IP and ER) [Aetna Medical Case]
- 10. Followup Time to First Stroke-Related Event (IP or ER) [Aetna Medical Case]
- 11. Followup Count of Systemic Embolic-Related ER Visits [Aetna Medical Case]
- 12. Followup Count of Systemic Embolic-Related IP Visits [Aetna Medical Case]
- 13. Followup Total Length of Stay for Systemic Embolic-Related IP Visits [Aetna Medical Case]

14. Followup Count of All Systemic Embolic-Related Visits (IP and ER) [Aetna Medical Case]
15. Followup Time to First Systemic Embolic-Related Event (IP or ER) [Aetna Medical Case]
16. Followup Count of Myocardial Infarction-Related ER Visits [Aetna Medical Case]
17. Followup Count of Myocardial Infarction-Related IP Visits [Aetna Medical Case]
18. Followup Total Length of Stay for Myocardial Infarction-Related IP Visits [Aetna Medical Case]
19. Followup Count of All Myocardial Infarction-Related Visits (IP and ER) [Aetna Medical Case]
20. Followup Time to First Myocardial Infarction-Related Event (IP or ER) [Aetna Medical Case]
21. Followup Diagnosis of Atrial Fibrillation [Aetna Claims Data]; [Aetna HPD]
22. Followup Mortality Aetna ATV; Aetna Membership Table
23. Followup Diagnosis of Alcoholism [Aetna HPD]
24. Followup Diagnosis of Benign Prostatic Hypertrophy [Aetna HPD]
25. Followup Diagnosis of Metastatic Cancer [Aetna Claims Data]
26. Followup Diagnosis of Cardiomyopathy [Aetna Claims Data]
27. Followup Diagnosis of Cataract [Aetna HPD]
28. Followup Diagnosis of Cerebrovascular Disorder [Aetna HPD]
29. Followup Diagnosis of Chronic Liver Disease [Aetna HPD]
30. Followup Diagnosis of COPD [Aetna HPD]
31. Followup Diagnosis of Chronic Renal Failure [Aetna HPD]
32. Followup Diagnosis of Chronic Thyroid Disorder [Aetna HPD]
33. Followup Diagnosis of Congestive Heart Failure [Aetna HPD]
34. Followup Diagnosis of Coronary Artery Disease [Aetna Claims Data]
35. Followup Diagnosis of Dementia [Aetna HPD]
36. Followup Diagnosis of Depression [Aetna HPD]
37. Followup Diagnosis of Diabetes Mellitus [Aetna HPD]
38. Followup Diagnosis of Glaucoma [Aetna HPD]
39. Followup Diagnosis of Hyperlipidemia [Aetna HPD]
40. Followup Diagnosis of Hypertension [Aetna HPD]
41. Followup Diagnosis of Anemia [Aetna Claims Data]
42. Followup Diagnosis of Ischemic Heart Disease [Aetna HPD]
43. Followup Diagnosis of Low Back Pain [Aetna HPD]
44. Followup Diagnosis of Nonspecific Gastritis/Dyspepsia [Aetna HPD]
45. Followup Diagnosis of Obesity [Aetna HPD]
46. Followup Diagnosis of Osteoarthritis [Aetna HPD]
47. Followup Diagnosis of Peripheral Vascular Disease [Aetna Claims Data]
48. Followup Diagnosis of Obstructive Sleep Apnea [Aetna Claims Data]
49. Followup Procedure: Cardioversion [Aetna Claims Data]
50. Followup Procedure: Catheter Ablation [Aetna Claims Data]
51. Followup Procedure: Maze Procedure [Aetna Claims Data]
52. Followup Procedure: Left Atrial Appendage Occlusion Procedure [Aetna Claims Data]
53. Followup Procedure: Coronary Artery Bypass Grafting [Aetna Claims Data]
54. Followup Procedure: Cardiac Stent(s) [Aetna Claims Data]
55. Followup Procedure: Valve Surgery [Aetna Claims Data]

56. Followup Procedure: Percutaneous Valve Procedures (Transcatheter Aortic Valve Replacement/TAVR, Transcatheter Mitral Valve Repair) [Aetna Claims Data]
57. Followup Procedure: Cardiac Transplant [Aetna Claims Data]
58. Followup Device: Cardiac Resynchronizing Therapy Device [Aetna Claims Data]
59. Followup Device: Left Ventricular Assist Device during Followup [Aetna Claims Data]
60. Followup Device: Pacemaker [Aetna Claims Data]
61. Followup Device: Defibrillator [Aetna Claims Data]
62. Followup Rx Fill for Digoxin [Aetna Pharmacy]
63. Followup Rx Fill for Beta Blocker [Aetna Pharmacy]
64. Followup Rx Fill for Calcium Channel Blocker [Aetna Pharmacy]
65. Followup Rx Fill for Antiarrhythmic Drug [Aetna Pharmacy]
66. Followup Rx Fill for ACE Inhibitor or ARB [Aetna Pharmacy]
67. Followup Rx Fill for Loop Diuretic [Aetna Pharmacy]
68. Followup Rx Fill for Spironolactone [Aetna Pharmacy]
69. Followup Rx Fill for Eplerenone [Aetna Pharmacy]
70. Followup Rx Fill for Nitrates/Hydralazine [Aetna Pharmacy]
71. Followup Rx Fill for Entresto [Aetna Pharmacy]
72. Followup Rx Fill for Statin or PCSK9 [Aetna Pharmacy]
73. Followup Rx Fill for P2Y12 Receptor Inhibitor [Aetna Pharmacy]
74. Followup Rx Fill for Diabetes Medication [Aetna Pharmacy]
75. Followup Rx Fill for Novel Anticoagulants [Aetna Pharmacy]
76. Followup Rx Fill for Other Anticoagulants [Aetna Pharmacy]
77. Followup Rx Fill for Warfarin [Aetna Pharmacy]
78. Followup Rx Fill for Heparin [Aetna Pharmacy]

Covariates

1. Sex [Aetna Membership Table]
2. Age [Aetna Membership Table]
3. Race/Ethnicity [Aetna Membership Table]
4. Insurance type (Medicare, Commercial or Both) [Aetna Membership Table]
5. Rural/suburban/urban (based on zip code) [Aetna Membership Table; U.S. Census]
6. Region of residence (based on zip code) [Aetna Membership Table; U.S. Census]
7. Median Household Income (based on zip code) [Aetna Membership Table; U.S. Census]
8. CHA₂DS₂ VASc [Aetna Claims Data; Aetna HPD; Calculation in Appendix]
9. Other co-morbidity scores
 - a. Baseline Episode Risk Group (Retrospective) [Aetna Predictive Modeling Table]
 - b. Baseline Episode Risk Group (Prospective) [Aetna Predictive Modeling Table]
 - c. Baseline Charlson Comorbidity Score [Aetna Claims Data]
 - d. Baseline Framingham Score [Aetna Claims Data; Aetna HPD]
10. Baseline months of Aetna Eligibility [Aetna Membership Table]

11. Follow-up months of Aetna Eligibility [Aetna Membership Table]
12. Total device wear time [Zio patch Usage]
13. Analyzable recording time [Zio patch Usage]

Baseline diagnoses:

14. Alcoholism [Aetna HPD]
15. Benign Prostatic Hypertrophy [Aetna HPD]
16. Metastatic Cancer [Aetna Claims Data]
17. Cardiomyopathy [Aetna Claims Data]
18. Cataract [Aetna HPD]
19. Cerebrovascular Disorder [Aetna HPD]
20. Chronic Liver Disease [Aetna HPD]
21. COPD [Aetna HPD]
22. Chronic Renal Failure [Aetna HPD]
23. Chronic Thyroid Disorder [Aetna HPD]
24. Congestive Heart Failure [Aetna HPD]
25. Coronary Artery Disease [Aetna Claims Data]
26. Dementia [Aetna HPD]
27. Depression [Aetna HPD]
28. Diabetes Mellitus [Aetna HPD]
29. Glaucoma [Aetna HPD]
30. Hyperlipidemia [Aetna HPD]
31. Hypertension [Aetna HPD]
32. Anemia [Aetna Claims Data]
33. Ischemic Heart Disease [Aetna HPD]
34. Low Back Pain [Aetna HPD]
35. Nonspecific Gastritis/Dyspepsia [Aetna HPD]
36. Obesity [Aetna HPD]
37. Osteoarthritis [Aetna HPD]
38. Peripheral Vascular Disease [Aetna Claims Data]
39. Obstructive Sleep Apnea [Aetna Claims Data]

Baseline procedures:

40. Cardioversion [Aetna Claims Data]
41. Catheter Ablation [Aetna Claims Data]
42. Maze Procedure [Aetna Claims Data]
43. Left Atrial Appendage Occlusion Procedure [Aetna Claims Data]

44. Coronary Artery Bypass Grafting [Aetna Claims Data]
45. Cardiac Stent(s) [Aetna Claims Data]
46. Valve Surgery [Aetna Claims Data]
47. Percutaneous Valve Procedures (Transcatheter Aortic Valve Replacement/TAVR, Transcatheter Mitral Valve Repair) [Aetna Claims Data]
48. Cardiac Transplant [Aetna Claims Data]
49. Cardiac Resynchronization Therapy Device [Aetna Claims Data]
50. Left Ventricular Assist Device during Baseline [Aetna Claims Data]

Baseline Prescriptions:

51. Digoxin [Aetna Pharmacy]
52. Beta Blocker [Aetna Pharmacy]
53. Calcium Channel Blocker [Aetna Pharmacy]
54. Antiarrhythmic Drug [Aetna Pharmacy]
55. ACE Inhibitor or ARB [Aetna Pharmacy]
56. Loop Diuretic [Aetna Pharmacy]
57. Spironolactone [Aetna Pharmacy]
58. Eplerenone [Aetna Pharmacy]
59. Nitrates/Hydralazine [Aetna Pharmacy]
60. Entresto [Aetna Pharmacy]
61. Statin or PCSK9 [Aetna Pharmacy]
62. P2Y12 Receptor Inhibitor [Aetna Pharmacy]
63. Diabetes Medication [Aetna Pharmacy]

Baseline Utilization

64. Outpatient visit [Aetna Medical Case]

